#### 2.17 Duration of treatment

The duration of the treatment will be 24 weeks in the first period with two weeks of washing after the treatment (week 24 to week 26). After this wash, the patient will undergo another 24 weeks (week 26 to week 50) of treatment corresponding to the second period and will end with another 2 weeks of wash (week 50 to 52).

In total, the trial will last 52 weeks, comprising two periods of 24 weeks of treatment each and 2 weeks of washing in each period.

#### 2.18 Schedule and expected completion date

The study is expected to begin, once the permits have been obtained, in a maximum time of 3 months from its acceptance to obtain the approval of the Spanish Regulatory Authority (AEMPS: Agencia Española del Medicamento y Productos sanitarios) and the Ethic Committee (CEIm: Comité Etico de Investigación con medicamentos)

The recruitment period will be 24 months from the activation of the center and the total follow-up of each patient will be 52 weeks spread over 18 visits. The study is expected to finish in December 2025.

- Start of trial (estimate): November 2021
- Recruitment period: 24 months
- End of recruitment (estimate): November 2023
- End of treatment of the last patient (estimate): November 2024
- End of follow-up period: 12 months after the last dose to the last patient
- End of the test. Estimate (estimate): December 2025

#### 3.- GENERAL INFORMATION

#### 3.1 Trial identification

Protocol Study: CAVES

EudraCT Number: 2021-001333-38

Version 1.0 10 Sep 2021

## 3.2 Type of clinical trial

Open-label, randomized, crossover, single-center clinical trial IIb / III to evaluate the efficacy of vortioxetine compared to standard treatment in recently diagnosed schizophrenia.

## 3.4 Description of the products of study

#### **Experimental treatment**

Generic name: Vortioxetine

Therapeutic Group: Psychoanaleptics; Other antidepressants

VORTIOXETINE is a multimodal antidepressant with a long duration of action. It is used in the treatment of cases of major depression. The mechanism of the antidepressant action of vortioxetine appears to be related to the direct modulation of serotonin receptor activity and the inhibition of the serotonin transporter. In vitro studies indicate that vortioxetine is an antagonist of the 5-HT3, 5-HT7 and 5-HT1D receptors, a partial agonist of the 5-HT1B receptor, a 5-HT1A receptor agonist. It which leads to modulation of neurotransmission in various systems, including predominantly serotonin, but probably also norepinephrine, dopamine, histamine, acetylcholine, GABA, and glutamate systems. This multimodal activity is believed to be responsible for the antidepressant and anxiolytic effects, as well as the improvement in cognitive function, learning, and memory observed with vortioxetine in animal studies.

# **Control treatment**

Generic name: antipsychotics used in routine clinical practice.

#### 4.- JUSTIFICATION

Comprehensive meta-analysis reviews consistently show marked impairments in a wide range of cognitive domains in schizophrenia, with considerable long-term effects. The effects tend to be somewhat higher especially for tests that assess memory and processing speed. The patients are cognitively outperformed by the controls at the onset of the disease, and the cognitive performance of the patients improves in a similar way to the controls over time (Rodriguez-Sanchez et al, 2013). Although the course of cognitive performance is generally stable, there is a subset of patients who experience cognitive decline over time. Patients whose cognitive performance experiences a decreasing trend show poorer progression in terms of clinical and disability variables.

The degree of baseline impairment in cognitive functions related to the prefrontal cortex are critical determinants of quality of life and functionality in schizophrenia (Treen Calvo et al. 2018 FEP). Therefore, cognition is an important goal of treatment, given the strong association between it and functional outcomes in people with psychotic disorders. Antipsychotics are quite effective in reducing the severity of positive symptoms and preventing relapse, but their impact on negative and cognitive symptoms is limited. In the last two decades, different strategies have been proposed to treat cognitive impairment in schizophrenia with uncertain achievements (Robbins et al, 2019). Cognitive enhancement agents are pharmaceuticals that are suggested to enhance cognitive performance by acting on the relevant neurotransmission systems, typically the glutamatergic and cholinergic systems. Results from individual studies have been mixed, and a recent metaanalysis of 93 studies, comparing cognitive enhancement agents with placebo, reported a small significant effect of cognitive enhancers on general cognition, but no significant effects on cognitive domains, individual. The main limitations are that many of these studies are underpowered to detect effects, that the number of studies investigating these agents is few, and the treatment durations are short (Sinkeviciute et al, 2018; Keefe et al, 2013).

The search for new cognitive treatments may be favored by the recognition of apparently analogous cognitive dysfunctions in different neuropsychiatric phenotypes. Therefore, cognitive impairments in schizophrenia could possibly be treated with a medication similar to that of Major Depressive Disorder (MDD), accepting that recurrent comorbidity in psychiatry can also extend to cognitive dimensions (Robbins, 2019).

The mechanism of action of Vortioxetine combines direct modulation of the 5-HT receptor (antagonist of 5-HT3, 5-HT7 and 5HT1D receptors, 5-HT1B receptor partial

agonist, 5-HT1A receptor agonist) and inhibition of the transporter of serotonin (5-HT): SERT inhibition. This target profile appears to consist of the modulated control of neuronal activity in key areas of the brain involved in Major Depressive Disorder, but also in the improvement of synaptic plasticity and cognitive function.

McIntyre et al (2014) reported cognitive improvement effects after 8 weeks of vortioxetine treatment, on a composite cognitive variable in depression. Importantly, the cognitive-enhancing effect was not associated with its mood-enhancing effects, suggesting the possibility of parallel effects on mood and cognition, through serotonergic actions.

Mahableshwarkar et al (2015) also identified that in adults with MDD who had reported cognitive dysfunction, vortioxetine significantly improved cognitive function, depression, and functionality, regardless of its effects on depressive symptoms.

Vortioxetine is a multimodal antidepressant similar to a SSRI in that it inhibits the serotonide transporter, but with additional actions on the 5-HT3 and 5-HT7 receptors, but it is not yet clear whether these contribute to cognitive enhancement effects and how. One suggestion has been that its 5-HT3 action may serve to disinhibit GABAergic receptors on interneurons (McIntyre et al, 2014).

Vortioxetine is approved for MDD in adults at a starting dose of 10 mg per day, which can be increased to 20 mg per day. Treatment providers may consider giving 5 mg daily for patients who cannot tolerate higher doses. Vortioxetine can be stopped abruptly, but a decrease to 10 mg per day is recommended for patients taking 15 mg per day or more for a week before complete discontinuation. Vortioxetine is in pregnancy category C. There are no data on its effects on lactation.

The two trial periods in which the patient receives the different treatments whose effects are being compared should be separated by a wash-out phase long enough to rule out any carry-over effects. In other words, the effect of the first treatment must have completely worn off before the start of the second period. With vortioxetine that period is 2 weeks.

#### 5.- HYPOTHESIS AND OBJECTIVES

# 5.1 Hypothesis

Our hypothesis is that adjuvant vortioxetine treatment could have a beneficial effect on cognitive symptoms and / or cognition in the early stages of patients with schizophrenia.

# 5.2 Objectives

- **5.2.1 Principal objective:** To investigate the effect of vortioxetine on cognitive functioning and the severity of negative symptoms in the early stages of schizophrenia, measuring the change in the BACS App Scale at the beginning and end of each period.
- **5.2.2 Secondary objective:** To assess the efficacy of vortioxetine versus TAU in treating negative symptoms in newly diagnosed schizophrenia, as measured by change in severity of negative symptoms (SANS total scores, NSA-4) from baseline to completion of the study.
  - Additionally, the following secondary objectives will be evaluated. To assess the efficacy of vortioxetine versus TAU in the treatment of cognitive deficits in recently diagnosed schizophrenia, as measured by change in general functioning (GAF total score)
  - To assess the safety of vortioxetine in recently diagnosed schizophrenia patients as measured by the reporting of any serious adverse event evaluated in relation to the Experimental Treatment during the 52 weeks of the trial.
  - Evaluate the efficacy and reliability of the BACS App Vs BACS, measured by performing both scales and comparing results. The purpose is to confirm the reliability of the results when performing the BACS App as a faster and more practical model at the beginning and end of each period (Measurement time: baseline visit, week 24, week 26 and week 50) compared to the results obtained with the BACS scale performed at each trial visit (Measurement time: from consent signature to week 52).

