# 2.12 Objectives

Principal objective: evaluate the efficacy of vortioxetine against TAU in the treatment of cognitive impairment in newly diagnosed schizophrenia, measured by the change from baseline to week 24 (and from week 26 to week 50 in the 2nd period) in the BACS App Scale scores, using the Composite Z Score defined as the weighted sum of the patient's Individual Z Score (frame time: baseline visit, week 24, week 26 and week 50).

Secondary objective: to evaluate the efficacy of vortioxetine against TAU in the treatment of negative symptoms in newly diagnosed schizophrenia, measured by the change in the severity of negative symptoms (SANS total scores, NSA-4) from baseline. until completion (frame time: baseline visit, week 4, week 12, week 24, week 26, week 30, week 38 and week 50).

Additionally the following secondary objectives will be evaluated To assess
the efficacy of vortioxetine versus TAU in the treatment of cognitive deficits in
newly diagnosed schizophrenia, as measured by change in general
functioning (GAF total score) (frame time: baseline visit, week 12, week 24,
week 26, week 38 and week 50)

Evaluate the safety of vortioxetine in patients with newly diagnosed schizophrenia measured through the communication of any serious adverse event evaluated in relation to the Experimental Treatment (frame time: from consent signature to week 52).

 Evaluate the efficacy and reliability of the BACS App Vs BACS, measured by performing both scales and comparing results. The purpose is to confirm the reliability of the results when performing the BACS App as a faster and more practical model at the beginning and end of each period (Measurement time: baseline visit, week 24, week 26 and week 50) compared to the results obtained with the BACS scale performed at each trial visit (Measurement time: from consent signature to week 52).

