# 6.1.2 Secondary endpoint

Secondary endpoints consist of improvement in the severity of negative symptoms as measured by the change in severity of negative symptoms on the SANS and NSA-4 score over the visits of each period (frame time: baseline visit, week 4, week 12, week 24, week 26, week 30, week 38 and week 50).

- Additionally the following secondary objectives will be evaluated. Functional
  improvement due to the change in general functioning measured by the GAF
  scale score from the beginning to week 24 of each period (frame time:
  baseline visit, week 12, week 24, week 26, week 38 and week 50)
- Safety assessment by measuring the frequency, severity, and relationship with study medication of any adverse event described during treatment. The reasons for withdrawal and / or abandonment of the trial will also be evaluated (if applicable): from the signing of the IC until week 52.

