#### 11.2 Definitions

#### Adverse Event (AE)

An adverse event is any unwanted medical reaction experienced by the patient at any time during the course of the study, whether or not it is considered to be related to the study treatment. This definition includes the appearance of a new disease and the exacerbation of pre-existing disorders other than the indication under study.

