# 11.4 Information of Adverse Events

The investigator will monitor and systematically collect the AEs related to study medication (ARs) starting from the signing of the Informed Consent Form until the final follow-up visit of each subject.

Also, the investigator will assess and record, in detail, the AR, including the start and dates, the description of the event, severity, course, outcome, and the measures taken (treatments, additional complementary examinations, etc).

The AR will be recorded in the medical history and recorded in the Case Report Form.

The subjects who present an AR will be subjected to relevant follow-up until duration of the same.

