#### 12.- STATISTICS

# 12.1 Sample size calculation

As it is a crossover design, each individual acts as their own control, that is, an initial treatment is assigned and after a while it is changed. Therefore, the correct thing to do would be to calculate the sample under the premise of related or paired samples, for this case it would be the dependent samples T test.

The sample size can be calculated in two ways, in the first one, the difference in the means to be detected of the primary variable (BACS), the standard deviations of the treatment change, and the correlation coefficient must be established; while the second is to consider the difference in the means to be detected for the primary variable (BACS) and the standard difference of the differences.

Accepting an alpha risk of 0.05 and a beta risk of 0.2 in a bilateral contrast, 37 subjects are required to detect a difference equal to or greater than 0.5 units. A standard deviation of 1 is assumed. A loss to follow-up rate of 15% has been estimated.

That is, based on the previous parameters, and using a confidence level of 95% and power of 80%, 37 subjects are needed.

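### The secondary safety objective counts serious adverse events over the whole trial, but its matching endpoint counts any adverse event during treatment; event class and window need one definition

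*Protocol*

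**What the plan says.** The protocol describes the same secondary safety item in several places.

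- **2.12 Objectives (synopsis):** safety is "measured through the communication of any serious adverse event evaluated in relation to the Experimental Treatment", with a time frame from consent to week 52.
- **5.2.2 Secondary objective:** safety is assessed "as measured by the reporting of any serious adverse event evaluated in relation to the Experimental Treatment during the 52 weeks of the trial".
- **6.1.2 Secondary endpoint:** "Safety assessment by measuring the frequency, severity, and relationship with study medication of any adverse event described during treatment". The next sentence adds the reasons for withdrawal and ends, after a colon, with a time frame from consent to week 52.
- **11.2 Definitions:** an adverse event counts "whether or not it is considered to be related to the study treatment". Serious adverse events are defined separately, by outcome criteria such as death, hospitalisation or disability.
- **11.4:** "The investigator will monitor and systematically collect the AEs related to study medication (ARs"), from consent to each subject's final follow-up visit.
- **Section 9 schedule:** the adverse-event row is marked at every visit from Visit 3 to Visit 18 and is empty at Visits 1 and 2. The visit lists in 9.1.1 and 9.1.2 agree with this.

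The washouts run from week 24 to 26 and from week 50 to 52 (8.1). No section gives an expected rate or number of adverse events, serious or not.

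**The concern.** An objective and its endpoint should name the same quantity. Here the objective is limited to serious events and the endpoint covers all events. Section 11.2 defines the two classes separately, and the serious-only wording appears in both the synopsis and the body, so it is hard to treat as a slip.

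The window differs as well. In this crossover every patient who completes has one washout directly after vortioxetine: weeks 24 to 26 if vortioxetine came first, weeks 50 to 52 if it came second. Whether an event that starts in those two weeks counts depends on which section is followed.

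Two things are at stake. The protocol itself expects tolerability problems: it allows dose reduction for tolerability (2.9, 8) and withdrawal for adverse events (7.3.2). A safety conclusion drawn from serious events alone would leave most of that out. And in an open-label trial, two available definitions allow one to be preferred after the data are seen.

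**Working it through.** **1. The definitions side by side.**

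| Section | Event class | Window |
|---|---|---|
| 2.12 | serious, evaluated in relation to vortioxetine | consent to week 52 |
| 5.2.2 | serious, evaluated in relation to vortioxetine | the 52 weeks |
| 6.1.2 | any, with severity and relatedness as outcomes | during treatment; reach of the consent-to-week-52 phrase unclear |
| 11.4 (collection) | related events only | consent to final visit |
| Section 9 schedule (collection) | adverse events, unrestricted | Visits 3 to 18 |

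Serious events are a subset of all events, so the objective can never count more patients than the endpoint over the same window. That direction needs no assumption.

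**2. The number of patients.** Section 12.1 gives 37, with two-sided alpha 0.05, power 80%, difference 0.5, standard deviation 1 and 15% loss. By the normal approximation for paired means:

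n = ((1.960 + 0.842) × 1 / 0.5)² = 31.4, and 31.4 / 0.85 = 36.9, so 37.

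The plan's figure reproduces. It already includes the allowance for loss, so about 37 × 0.85 = 31.45 patients are expected to complete. Dropouts are not replaced (2.13, 6.6), and a patient randomised to TAU first who leaves early never receives vortioxetine. On this sample size 37 is therefore a ceiling on the number exposed.

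**3. What the serious-only definition would yield.** Let p be the share of patients with at least one serious event. It is assumed, because the protocol gives none. Expected patients = N × p; chance of seeing none = (1 − p)^N.

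| Assumed p | N = 37: expected | N = 37: P(none) | N = 31.45: expected | N = 31.45: P(none) |
|---|---|---|---|---|
| 1% | 0.4 | 0.69 | 0.3 | 0.73 |
| 3% | 1.1 | 0.32 | 0.9 | 0.38 |
| 5% | 1.9 | 0.15 | 1.6 | 0.20 |
| 10% | 3.7 | 0.02 | 3.1 | 0.04 |

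If no serious event is seen, the one-sided 95% upper limit on the risk is 1 − 0.05^(1/37) = 7.8% with 37 exposed, and 1 − 0.05^(1/31) = 9.2% with 31.

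**4. What the any-event definition would yield.** At an assumed share of 30% to 70%, 37 × 0.30 = 11.1 to 37 × 0.70 = 25.9 patients.

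**5. Sensitivity to N.** Section 2.16 speaks of recruiting 50. With 50 exposed, 1% to 10% gives 0.5 to 5.0 patients with a serious event, which is still few.

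**6. Can the endpoint be obtained?** Under 11.4, unrelated events need not be collected systematically, yet 6.1.2 treats relatedness as something to be measured across all events. A window from consent also has no scheduled adverse-event review at Visits 1 and 2.

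**The case against.** The best reply is that 6.1.2 is the endpoint section and already requires all adverse events, and that adverse events are reviewed at every visit from Visit 3, including weeks 26 and 52, which close the washouts. Vital signs and laboratory tests are safety assessments too (11.1). This stands: a report that follows 6.1.2 would show non-serious events. A reader might infer that tolerability problems will go unreported; the documents do not support that. They support only that the stated objective could be met without reporting them.

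Three other stronger readings also fail.

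- A reader might infer that the two definitions give about one event against many. The protocol contains no rates. About one patient needs an assumed serious-event share near 3%, and the any-event count is equally an assumption.
- A reader might say that 6.1.2 contradicts itself on the window. Its consent-to-week-52 phrase follows the sentence on withdrawals and may cover only those, or the whole item. That is ambiguity. The clear mismatch is between the treatment-only wording in 6.1.2 and the windows in 2.12 and 5.2.2, and for washout events it depends on reading that wording literally.
- A reader might take 37 as the number exposed. It is the planned total before loss.

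It can also be said that tabulation by period belongs in the SAP, which is not at hand. That is fair for the table layout. It does not cover the event class and window, which the protocol states differently in its own objective and endpoint.

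**Conclusion.** The inconsistency is real: the objective (2.12, 5.2.2) and the endpoint (6.1.2) name different event classes and, read literally, different windows. The textual finding rests on no assumption. Its practical size does: at an assumed serious-event risk of 1% to 10%, the objective alone would rest on at most 0.4 to 3.7 patients among no more than 37, too few to show or exclude a tolerability problem.

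The matter should be corrected, but its weight is moderate. It concerns a secondary safety outcome and leaves the primary endpoint, the sample size and the efficacy analysis untouched.

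**What to change.** - **One event set in 2.12, 5.2.2 and 6.1.2:** patients with any adverse event, by severity, seriousness and relatedness, with serious events as a subset, plus reasons for withdrawal.
- **One window:** consent to week 52, stated in all three sections. The schedule labels the final visit week 52 but dates it Day 379, whereas on its own count 52 × 7 + 1 = 365. These need reconciling so that the window has one end date.
- **Tabulation by period of onset:** vortioxetine, TAU, or the washout after each. The detail can sit in the SAP.
- **Collection:** extend 11.4 to all adverse events with relatedness recorded, and add an adverse-event entry at Visits 1 and 2 in the schedule and in 9.1.1 and 9.1.2. Changing only the objectives would leave an endpoint that the collection rules do not clearly support.

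The cost is wording in those sections, some extra recording of unrelated events and one added table breakdown. No extra visits or patients are needed.

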#### 6.- STUDY DESIGN

## 6.1 Endpoints

## 6.1.1 Principal endpoint

The primary endpoint of the response consists of the improvement in cognitive functioning as assessed by the change in the BACS App Scale score: changes from baseline to week 24 (and from week 26 to week 50 in the 2nd period) in the scores of the BACS App Scale, using the Composite Z Score defined as the weighted sum of the patient's Individual Z Score (frame time: baseline visit, week 24, week 26 and week 50).

# 6.1.2 Secondary endpoint

Secondary endpoints consist of improvement in the severity of negative symptoms as measured by the change in severity of negative symptoms on the SANS and NSA-4 score over the visits of each period (frame time: baseline visit, week 4, week 12, week 24, week 26, week 30, week 38 and week 50).

- Additionally the following secondary objectives will be evaluated. Functional
  improvement due to the change in general functioning measured by the GAF
  scale score from the beginning to week 24 of each period (frame time:
  baseline visit, week 12, week 24, week 26, week 38 and week 50)
- Safety assessment by measuring the frequency, severity, and relationship with study medication of any adverse event described during treatment. The reasons for withdrawal and / or abandonment of the trial will also be evaluated (if applicable): from the signing of the IC until week 52.

